Venous thromboembolism: After the data cut-off date for inclusion in the above review of emerging safety data, a number of AE reports of venous thromboembolism (pulmonary embolism, and deep vein thrombosis) were received for patients in study D5860C00001. By 18 August 2015 there were a total of 4 events of Grade 3 pulmonary embolism in 4 patients reported to AstraZeneca for patients in study D5860C00001. At that date, 29 patients had been treated with IONIS-AR-2.5_{Rx} in that study. Of the 4 patients, 3 were symptomatic (and were incidental findings on routine CT restaging), and 1 patient presented with shortness of breath. All patients continued on study after diagnosis and treatment. Initially 2 of these events were assessed as unrelated to IONIS-AR-2.5_{Rx} by the site investigators, but considering the cluster of pulmonary embolism events, AstraZeneca reassessed these events as possibly related to study therapy. In addition, 3 other events of non-serious deep venous thrombosis were reported, and constitute similar thromboembolic phenomena.

Marketing experiences:

IONIS-AR-2.5_{Rx} 2 is an investigational drug and is not available as a marketed product in any region.

Emerging safety profile:

This section is the Reference Safety Information for IONIS-AR-2.5_{Rx} and presents those events that are to be regarded as expected for safety reporting purposes:

Venous thromboembolism (pulmonary embolism and deep vein thrombosis) – Occurs at a Council for International Organizations of Medical Sciences (CIOMS) III frequency of very common (>10%). The majority of pulmonary embolism reports were incidental.

SUMMARY OF DATA AND GUIDANCE FOR THE INVESTIGATORS:

Contraindications

IONIS-AR-2.5_{Rx} is an investigational drug and should only be used in accordance with the relevant clinical protocol. Patients must fulfil the Inclusion Criteria and not violate any of the Exclusion Criteria specified within the relevant protocol.

Warnings and precautions

Pregnancy

Reproductive and developmental toxicity studies and juvenile toxicity studies have not been conducted with IONIS-AR-2.5_{Rx} to date, and it is unknown whether the drug is excreted in human milk. Therefore, men taking IONIS-AR-2.5_{Rx} and their female partners of childbearing potential should agree to use adequate contraception for the duration of study participation, and for 120 days following last study treatment.

Male subjects should be fully informed of the lack of reproductive toxicity testing. The clinical protocol gives details on the requirements to report pregnancy and its outcome.

Interaction potential

No interaction studies have been conducted with IONIS-AR-2.5_{Rx} to date.

Phosphorothioate oligonucleotides are not substrates for the classic CYP metabolic pathways and are thus unlikely to interact with other drugs that modulate or are modulated by CYP, and the same would again be expected for IONIS-AR-2.5_{Rx}, though not yet evaluated.

Overdose

IONIS-AR-2.5_{Rx} must only be used in accordance with the relevant clinical protocol. An overdose is defined as a dose of IONIS-AR-2.5_{Rx} 2 administered to a patient that is greater than the protocol defined dose for the patient. Symptomatic and non-symptomatic overdose must be documented in accordance with the protocol.

There is currently no specific treatment in the event of an overdose with IONIS-AR-2.5_{Rx} and possible symptoms of overdose have not been established. In the event of overdose, the patient should be observed and appropriate symptomatic treatment given.

IONIS-AR-2.5_{Rx} toxicity observed in preclinical studies

The anticipated AE profile and potential risks seen with IONIS-AR-2.5_{Rx}²² in mice and monkeys, include accumulation of compound as basophilic granules in multiple tissues, complement activation and prolongation of activated partial thromboplastin time (aPTT) in monkeys and pro-inflammatory effects in mice are consistent with expected effects of ASOs (Burel et al 2013).²²

Evidence of effects on AR signaling, including tissue weight and histopathological changes, are in line with expected pharmacodynamics.

Safety considerations for phosphorothioate oligonucleotides.

More than twenty 2'-MOE-modified phosphorothioate ASOs, a chemical class similar to IONIS-AR-2.5_{Rx}, have been administered to human subjects, including ASOs that are under evaluation for the treatment of cancer. Clinical safety results of such 2'-MOE-modified ASOs can provide guidance to the potential attributes of IONIS-AR-2.5_{Rx}. Some profile differences exist between class members and extrapolations from one ASO to another should be made cautiously^{23,24}.

Potential class-related effects are informed by prior clinical experience with IV-administered 2nd generation ASOs and include transient constitutional symptoms associated with early doses and transient prolongation of aPTT²⁴. Also, due to prior preclinical findings for one or more members of the drug class, the following additional areas are monitored in the clinical trials of ASOs: renal effects, liver effects, complement activation, and proinflammatory effects^{23,24}.

Constitutional symptoms

Transient fever, chills, body aches, nausea, and other constitutional symptoms have been experienced following the first few administrations of some ASOs²⁴. In general, these symptoms appear within hours of ASO administration, are mild in intensity, and resolve spontaneously overnight. The occurrence and intensity of these symptoms generally diminishes over the course of repeated administrations. The proportion of patients that experience infusion-associated constitutional symptoms and the symptom spectrum is dose dependent.

At doses in the range of 200 to 400 mg, mild body aches, and general discomfort are the most frequent complaints. However, at higher doses, fever and chills become more prominent complaints. The relationship between dose and constitutional symptoms is variable between ASOs.

Constitutional symptoms associated with dose administration should be monitored through adverse event recording, and should be managed as required.

Prolongation of aPTT

Prolongation of aPTT associated with ASO administration has been shown to be the result of low-affinity oligonucleotide binding to the tenase complex (Factor IXa-Factor VIIIa phospholipid) and the effect is proportional to concentration of oligonucleotide in plasma (C_{max})^{24,25}. In monkeys, there were acute, transient increases in aPTT at 12 mg/kg IONIS-AR-2.5_{RX} and above. There was no evidence of associated hemorrhage or bleeding. Changes in activity of the intrinsic clotting pathway reverse when ASO is cleared from plasma. Coagulation effects should be monitored by adverse event recording.

Renal effects

The kidney is the organ of greatest ASO distribution. The dose-dependent presence of basophilic granules in proximal tubular epithelial cells is a common finding for animals treated with ASOs²³. They arise from the accumulation of ASOs in endosomal vesicles and as such are an indication of ASO uptake and compartmentalization.

No toxicological effects have been associated with the presence of basophilic granules. Renal effects should be monitored through adverse event recording, clinical chemistry evaluations, and urinalysis.

Liver effects

The liver is the organ having the second highest distribution of ASOs. In humans and monkeys, elevations of transaminases or other signs of hepatotoxicity are not a class-effect of phosphorothioate oligonucleotides. Two to three-fold increases in transaminases are routinely observed in mice and other rodents; however, the elevations are secondary to the proinflammatory effects of ASOs in this most sensitive species (manifested by inflammatory cell infiltrates in multiple organs including the liver). In some cases, liver enzyme elevations have occurred after administration of oligonucleotides in humans.

Liver effects should be monitored through adverse event recording and clinical chemistry parameters.

Complement activation

Complement pathway activation has been observed in monkeys treated with high doses of phosphorothioate oligonucleotides. The effect arises from the interaction of oligonucleotides with Factor H, an inhibitor of complement activation, and occurs when oligonucleotide levels in plasma exceed threshold concentrations (approximately >100 µg/mL for most ASOs after IV administration)^{23,26}. Monkeys are known to be more sensitive to complement activation than humans²⁷.

Proinflammatory effects

Pro-inflammation is a well described non-specific class effect of ASOs^{28,29}. In preclinical toxicology studies, particularly in studies conducted in rodents, proinflammatory effects are often observed for the phosphorothioate oligonucleotide chemical class. In general, rodents appear to be more sensitive to ASO-mediated pro-inflammatory effects than primates²³.

Pro-inflammatory effects should be monitored by adverse event recording.

9.2 Enzalutamide

Other names for the drug: XTANDI®

Description:

Enzalutamide is a white crystalline non-hygroscopic solid. Enzalutamide is provided as a liquid-filled soft gelatin capsule for oral administration. Each capsule contains 40 mg of enzalutamide as a solution in caprylocaproyl polyoxylglycerides.

Classification: type of agent: androgen receptor inhibitor

Mode of action:

Enzalutamide is an androgen receptor inhibitor that acts on different steps in the androgen receptor signaling pathway. Enzalutamide has been shown to competitively inhibit androgen binding to androgen receptors and inhibit androgen receptor nuclear translocation and interaction with DNA.

Pharmacokinetics:

Absorption: rapid with time to peak concentration in 1 hour (range 0.5-3 hours). A high-fat meal did not alter the AUC to enzalutamide or N-desmethyl enzalutamide.

Distribution: 110 L; protein binding of parent drug is 97-98% to primarily albumin; protein binding of active metabolite is 95% to plasma proteins

Metabolism: Hepatic via CYP2C8 (formation of active metabolite N-desmethyl enzalutamide) and CYP3A4

Excretion: Primarily eliminated by hepatic metabolism. Following single oral administration of 14C-enzalutamide 160 mg, 85% of the radioactivity is recovered by 77 days post dose: Urine (71%), feces (14%) primarily as inactive metabolite

T1/2: Enzalutamide: 5.8 days (range 2.8-10.2 days); N-desmethyl enzalutamide: 7.8-8.6 days.

Side effects:

The most common adverse reactions ($\geq 10\%$) are asthenia/fatigue, back pain, decreased appetite, constipation, arthralgia, diarrhea, hot flush, upper respiratory tract infection, peripheral edema, dyspnea, musculoskeletal pain, weight decreased, headache, hypertension, and dizziness/vertigo.

Drug Interactions: Please refer to the package insert for enzalutamide.

Storage and stability: Store enzalutamide at 20° to 25°C (68° to 77°F) in a dry place and keep the container tightly closed. Excursions permitted to 15° to 30°C (59° to 86° F).

Administration:

Enzalutamide is administered orally once daily with or without food for 21 day cycles. Patients should be instructed to swallow capsules whole, and not to open or crush the capsules. Subjects will be asked to keep a pill diary noting the date they take enzalutamide. They will be asked to bring their pill diary on day one of each cycle and all used and unused medication bottles and remaining pills in the bottle(s) will be counted to document compliance. This information should be recorded on the patient's pill diary and/or in the patient data file.

Availability: Commercially available

Drug Accountability:

The investigator, or a responsible party designated by the investigator, must maintain a record of the disposition of enzalutamide. The drug accountability records should capture drug dispensing, drug return and final disposition.

10.0 CORRELATIVES/SPECIAL STUDIES

The goal of the planned laboratory correlative studies is to ascertain if ISIS 560131 effectively inhibits AR signaling in the tissues, confirm its mechanism of action as postulated, profile the tumor cell intracellular pathways and understand mechanisms of resistance.

- Submission of tissue samples for correlative studies is mandatory at baseline (archival/fresh biopsy).

- Submission of tissue samples for correlative studies is optional at 2 cycles post therapy and at progression.
- Whole blood samples collected at C1D1 pre-dose will be banked for possible future analysis including to identify potential molecular biomarkers that may be indicative of clinical response/resistance. Refer to Lab Manual.
- Blood samples will be collected pre and post dose of IONIS-AR-2.5_{Rx} for pharmacokinetic analysis for the first two cycles only. Plasma PK samples may also be used for profiling of drug binding proteins, bioanalytical method development and/or validation purposes, stability assessments, metabolite assessments, immunogenicity assessments or to assess other actions of IONIS-AR-2.5_{Rx} with plasma constituents. Refer to Lab Manual.

10.1 Sample Collection Guidelines (Refer to Lab Manual).

Tumor Tissue

Tumor tissue should be processed and shipped to the Michigan Center for Translational Pathology (below). From each patient, tissue specimens will be collected at time points indicated in the Study Calendar. Generally, tissue specimens will be collected from:

- a. A metastatic site of disease (via biopsy) or adequate metastatic tissue from prior biopsy or resection.
- b. Archived prostatectomy or biopsy specimen from the primary prostate tumor (if available, via retrieval of previously archived specimens).

Archived Prostate Cancer Samples:

Occasionally, castration resistant prostate cancer tissue may have been obtained previously for the subject and archived. This tissue may be utilized for baseline tissue purposes.

- If resection specimens are available (preferred): The block with the highest volume of representative tumor histology from the index focus OR 16 unstained, unbaked sections (4-5 microns in thickness) on glass slides (charged or uncharged) should be shipped at room temperature to the University of Michigan.
- If biopsy specimens are available: Three blocks with the highest volume of representative tumor histology OR 15 unstained, unbaked sections (4-5 microns in thickness) on glass slides (charged or uncharged) from up to three blocks should be shipped at room temperature to the University of Michigan. If unstained sections are sent, they should be labeled with the block number/letter. If less than three blocks have cancer, then all blocks with cancer OR as many unstained sections as can be cut from blocks with cancer without exhaustion should be sent.

Whole blood and PK Plasma IONIS-AR-2.5_{Rx} Samples:

Whole blood and PK plasma samples should be processed and shipped according to the Lab Manual.

11.0 STATISTICAL CONSIDERATIONS

This is a single dose-finding one-arm, phase Ib/II trial to (i) estimate the MTD from among three dose levels of IONIS-AR-2.5_{Rx} in combination with a fixed dose of enzalutamide, as described below, and (ii) obtain preliminary estimate of efficacy at this estimated MTD, as measured by PSA response rate. The MTD is defined as the highest dose of IONIS-AR-2.5_{Rx} inducing a rate of DLT closest to but not larger than 35%, and we will assess the evidence that the PSA response rate at

this dose level exceeds 5%. The planned enrollment is 35 evaluable patients. Success for the trial is defined as finding a dose level that is likely to be both tolerable and effective.

There are two novel elements relative to standard Phase Ib/II designs. First, statistical-model-based between-patient dose modifications of IONIS-AR-2.5_{Rx} accounting for cumulative toxicity outcomes will be implemented during the entire trial. Second, instead of using only patients at the MTD to determine the PSA response rate, a monotonic model of PSA response using all response evaluable patients will be used to estimate the PSA response rate at the MTD. The only formal statistical mechanism for stopping the trial early is due to exceeding toxicity (safety) thresholds.

11.1 Study Design

Dose Assignment in Phase 1b: The first patient will be enrolled to dose level 3 of IONIS-AR-2.5_{Rx}, in combination with a fixed dose of enzalutamide. Subsequent dose assignments to dose levels 1, 2 or 3 will be based upon the statistical-model-based TITE-CRM design. This trial will seek to estimate the MTD, the true value of which is defined as the dose level with probability of DLT closest to but not exceeding 35%.

Final Efficacy Analysis After all 35 evaluable patients are enrolled and the PSA response endpoint is recorded for all patients, we will fit the Bayesian isotonic regression model on all patients' data. If the probability that the PSA response rate at the final estimated dose exceeds 5% is at least 0.95, the trial will have successfully completed its primary objective.

Interim Analysis/Criteria for Stopping Study Continuous monitoring of safety is built into the TITE-CRM model, and the trial will stop at any point in which all dose levels have a model-estimated probability of DLT exceeding 37.5%.

11.2 Endpoints

11.2.1 Primary Endpoints

The primary endpoints are (i) dose-limiting toxicity (DLT) during the first cycle of IONIS-AR-2.5_{Rx} (in combination with enzalutamide) and (ii) PSA response (PSA decline of 50% or greater from baseline) at any time after the start of combination therapy.

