	
Primary Endpoint
 
 1. Dose-limiting toxicity (DLT) and MTD during the first cycle of IONIS-AR-2.5Rx (in combination with enzalutamide) 2. PSA decline of 50% or greater from baseline using PCWG3 criteria at any time after the start of combination therapy 
Secondary Endpoints
 
 1. Efficacy: Radiographic progression-free survival time (rPFS) by PCWG3-modified RECIST 1.1, PSA progression-free survival time, PSA reductions by 30% and 50% from baseline, duration of therapy (DOT), duration of PSA Response (DOR), and overall survival time 2. Safety and toxicity: Adverse events as assessed by CTCAE criteria 5.0 and classified by body system, grade and attribution. Other toxicity endpoints include intrapatient dose delays and dose reductions. 
Exploratory/Correlative Endpoints
 
 1. Androgen receptor driven signaling measures in tumor tissues 2. Measures of genomic metabolomics and proteomic biomarkers in blood and tissues 3. FACT-P and EuroQoL-5D scores with comparisons to baseline scores 4. Pharmacokinetic (PK) characteristics
Number of Subjects	35 evaluable subjects

Protocol UMCC 2017.055

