2.4 Primary Endpoint

- 2.4.1 Dose-limiting toxicity (DLT) during the first cycle of IONIS-AR-2.5_{Rx} (in combination with enzalutamide)
- 2.4.2 PSA decline of 50% or greater from baseline using PCWG3 criteria at any time after the start of combination therapy

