5.3 Concomitant Medications/Treatments

Medications or vaccinations specifically prohibited in the exclusion criteria are not allowed during the ongoing trial. If there is a clinical indication for any medication or vaccination specifically prohibited during the trial, discontinuation from trial therapy or vaccination may be required. The investigator should discuss any questions regarding this with the Study PI. The final decision on any supportive therapy or vaccination rests with the investigator and/or the subject's primary physician. However, the decision to continue the subject on trial therapy or vaccination schedule requires the mutual agreement of the investigator, the Sponsor and the subject.

Use of bisphosphonates/RANKL inhibitors are standard in CRPC and are allowed on the study.

Subjects are prohibited from receiving the following therapies during the Screening and Treatment of this trial:

- Antineoplastic systemic chemotherapy or biological therapy except for ongoing androgen deprivation therapy (e.g. with LHRH agonist/antagonist)
- Immunotherapy
- Chemotherapy not specified in this protocol
- Investigational agents
- 5 α -reductase inhibitors (e.g., finasteride, dutasteride).
- Any herbal product known to decrease PSA levels (eg. Saw Palmetto and PC-SPES)
- Neulasta[®]
- Radiation therapy
 - Local intervention is discouraged unless medically unavoidable. Radiation therapy to a symptomatic solitary lesion/area may be considered on a

case-by-case basis after consultation with the Principal Investigator (except during screening). Subjects receiving local intervention (e.g., palliative radiation) are allowed to continue to receive study treatment at the investigator's discretion. Subjects who receive local intervention may be considered not evaluable (and may be assigned a conservative censoring or progression date).

- Live vaccines within 30 days prior to the first dose of treatment and while participating in the trial. Examples of live vaccines include, but are not limited to, the following: measles, mumps, rubella, varicella/zoster, yellow fever, intranasal influenza, rabies, BCG (tuberculosis vaccine), and typhoid vaccine.
- Systemic glucocorticoids or other immunosuppressive drugs for any purpose other than to modulate symptoms from a drug-related AE of immunologic etiology (refer to Section 5.2 – Dose Modification). The use of physiologic doses of corticosteroids may be approved after consultation with the Study PI.

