5.7 Duration of Follow-Up

Patients will be followed for up to 24 months after removal from treatment or until death, whichever occurs first. Patients removed from treatment for unacceptable adverse events will be followed until resolution or stabilization of the adverse events.

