6.0 STUDY PROCEDURES

Time and Events Table

All assessments have a window of \pm 3 business days except for imaging/tumor measurements where a window of \pm 7 business days will apply or unless otherwise specified.

Cycle length = 21 days

Trial period	Screening	Treatment								Safety Follow-up/EOT	Follow-up Visits
Treatment Cycle/Title	Screening Visit	Cycle 1								30 days from last dose of IONIS-AR-2.5Rx (+/- 7 business days)	Every 12 weeks (+/- 7 business days) For up to 24 months
Scheduling Window (Days)	-28 to -1	D 1	D 4	D 8	D 11	D 15	D 1	D 8	D 15		
Administrative Procedures:											
Informed Consent	X										
Review Eligibility Criteria	X										
Demographics and Medical History	X	X	X	X	X	X	X	X	X		
Prior and Concomitant Medications	X	X	X	X	X	X	X	X	X		
Survival Status											X ⁶
Clinical Assessments:											
Review Adverse Events	X	X	X	X	X	X	X	X	X		
Physical Examination	X	X		X		X	X				
Vital Signs		X	X	X	X	X	X	X	X		
Height ⁵ , Weight	X	X					X				X
ECOG Performance Status	X	X					X				X
Laboratory Assessments:											
PT/INR and PTT/aPTT	X	X		X		X	X	X	X		
CBC with differential, platelets	X	X	X	X	X	X	X	X	X		
Comprehensive Metabolic Panel ¹ , D-dimer	X	X	X	X	X	X	X	X	X		
PSA	X	X					X			X	X
Testosterone	X	X								X	
TSH, free T3, free T4 (If Clinically Indicated: FSH, LH, ACTH)	X									X	
Treatment:											
IONIS-AR-2.5Rx ⁴		X	X	X	X	X	X	X	X		
Enzalutamide		PO daily in 21-day cycles									

Trial period	Screening	Treatment								Safety Follow-up/EOT	Follow-up Visits
Treatment Cycle/Title	Screening Visit	Cycle 1								30 days from last dose of IONIS-AR-2.5Rx (+/- 7 business days)	Every 12 weeks (+/- 7 business days) For up to 24 months
Scheduling Window (Days)	-28 to -1	D 1	D 4	D 8	D 11	D 15	D 1	D 8	D 15		
Imaging Tumor Assessments²											
CT chest/CXR	X									X	X
MRI Abdomen/Pelvis or CT Abdomen/Pelvis	X									X	X
Bone Scan	X									X	X
QoL questionnaires³		X					X			X	
Correlatives											
Whole blood for banking		X pre-dose									
Tumor Tissue Archival CRPC	X										
Tumor Tissue Biopsy ⁷	X							X		X	
PK Plasma IONIS-AR-2.5Rx concentration (pre-dose) ^{8,10}		X	X	X	X	X	X	X			
PK Plasma IONIS-AR-2.5Rx concentration (end of infusion) ^{8,9,10}		X	X	X	X	X	X	X			

1. Comprehensive metabolic panel (CMP) to include: albumin, alkaline phosphatase, ALT/SGPT, AST/SGOT, BUN, creatinine, electrolytes (sodium, potassium, calcium, chloride, bicarbonate), glucose, and total bilirubin; LDH, D-dimer.

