7.1.1 Definitions

Evaluable for toxicity. All patients will be evaluable for toxicity from the time of their first treatment with IONIS-AR-2.5Rx.

Evaluable for PSA response. Only those patients who have received at least 1 dose of IONIS-AR-2.5Rx, and have at least 2 PSA measures at least 1 week apart after initiating treatment will be considered evaluable for PSA response. (Note: Patients who exhibit objective disease progression prior to the end of cycle 2 will also be considered evaluable and will be classified as PSA non-response).

Evaluable for objective response. Only those patients who have measurable disease present at baseline, have received at least 1 dose of IONIS-AR-2.5Rx, and have had their disease re-evaluated will be considered evaluable for objective response. These patients will have their response classified according to the definitions stated below. (Note: Patients who exhibit objective disease progression prior to the end of cycle 4 will also be considered evaluable).

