7.2.2 PSA Response

Per PCWG3 criteria, PSA response rate will be defined as the proportion of subjects who have a PSA response defined by a 50% decline or more in PSA (ng/ml) from baseline measured twice at least 3 weeks apart. Based on the PCWG3 criteria, a favorable effect on PSA may be delayed for ≥ 12 weeks. PSA will be monitored every cycle, but treatment will be planned to continue through early rises for 12 weeks unless other evidence of progression, such as radiographic progression. Therefore, early rises in PSA before 12 weeks will not be considered progression when determining PSA response.

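### Section 11.2.1 omits the PSA confirmation that 7.2.2 requires, and apart from early objective progressors no passage explicitly closes the response window

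*Combined protocol and SAP*

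**What the plan says.** **Confirmation.** The primary efficacy endpoint in 11.2.1 is "PSA response (PSA decline of 50% or greater from baseline) at any time after the start of combination therapy". It mentions neither a second measurement nor PCWG3, and does not refer to 7.2.2. Section 2.4.2 has "PSA decline of 50% or greater from baseline using PCWG3 criteria at any time after the start of combination therapy", and the synopsis has the same. Section 7.2.2 defines PSA response, per PCWG3, by a 50% "decline or more in PSA (ng/ml) from baseline measured twice at least 3 weeks apart". The synopsis also lists "PSA reductions by 30% and 50% from baseline" among the secondary endpoints. Section 11.6.1 counts PSA responders without saying which definition applies.

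**Window.** The one explicit closing rule is in 7.1.1: patients with "objective disease progression prior to the end of cycle 2 will also be considered evaluable and will be classified as PSA non-response". Section 7.2.2 adds that PSA rises in the first 12 weeks are not treated as progression when response is determined, and 7.2.5 measures duration of response up to progression. On follow-up, 5.7 says: "Patients will be followed for up to 24 months after removal from treatment or until death, whichever occurs first". The Time and Events Table marks PSA at the follow-up visits, which take place "Every 12 weeks (+/- 7 business days) For up to 24 months". Section 5.3 introduces its list of barred treatments with "Subjects are prohibited from receiving the following therapies during the Screening and Treatment of this trial". Section 11.1 runs the final analysis once the endpoint has been recorded for every patient, but does not say when a non-responder's status is final.

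**The concern.** An analyst working from Section 11 would count a single low PSA value that 7.2.2 would not accept.

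Adopting 7.2.2 does not settle the window. Two follow-up values 12 weeks apart, both taken on a later drug, are more than 3 weeks apart and so confirm each other. Taken literally, that fall is credited to IONIS-AR-2.5Rx plus enzalutamide.

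The trial has one arm, so no control group would show the misattribution. It is open label, so if definition and window stay open, they could be chosen after the data have been seen. What is at stake is the reported response rate and, near the boundary, whether success is declared.

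**Working it through.** **Inputs (11.1, 11.3, 11.6.1).** N = 35. Priors are Beta(0.1, 1.9), Beta(0.3, 1.7) and Beta(0.5, 1.5) for levels 1 to 3, constrained to m1 ≤ m2 ≤ m3. Success means P(m at the MTD > 0.05 | data) ≥ 0.95.

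**The plan's own figures first.** A simulation of the 11.6.1 design (TITE-CRM, then the constrained Beta posterior; 33 patients a year and response independent of DLT assumed) was compared with the first row of Table 1B, DLT {8%, 13%, 25%}:

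| PSA response set | Table 1B | Simulated |
|---|---|---|
| {3%, 8%, 10%} | 0.47 | 0.44–0.46 |
| {5%, 13%, 20%} | 0.92 | 0.91 |
| {5%, 10%, 25%} | 0.94 | 0.96 |
| {20%, 28%, 35%} | 0.99 | 0.99 |

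The first row of Table 1A (0.97) is also reproduced.

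**Success boundary.**

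| Allocation | MTD | Responders | Posterior probability | Result |
|---|---|---|---|---|
| 35 at level 3 | 3 | 3 | 0.88 | fail |
| 35 at level 3 | 3 | 4 | 0.96 | succeed |
| 5 at level 2, 30 at level 3 | 3 | 0 + 3 | 0.91 | fail |
| 5 at level 2, 30 at level 3 | 3 | 1 + 3 | 0.967 | succeed |
| 25 at level 2, 10 at level 3 | 2 | 4 + 1 | 0.945 | fail |
| 25 at level 2, 10 at level 3 | 2 | 4 + 2 | 0.965 | succeed |

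With all 35 at level 3, success is therefore X ≥ 4 with X ~ Bin(35, p). One wrongly counted patient decides the result only when the counted total is exactly 4. P(X = 4) is 0.200, 0.172, 0.083, 0.027 and 0.0012 at p = 10%, 15%, 20%, 25% and 35%.

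**Open window.** Suppose later therapy produces a qualifying fall in a share q of non-responders. The documents give no rate, so q is an assumption. The counted rate becomes p + (1 − p)q; for example 0.05 + 0.95 × 0.05 = 0.0975. P(X ≥ 4), all at level 3:

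| True rate p | q = 0 | q = 2% | q = 5% | q = 10% |
|---|---|---|---|---|
| 5% | 0.096 | 0.220 | 0.449 | 0.767 |
| 10% | 0.469 | 0.605 | 0.767 | 0.921 |
| 20% | 0.939 | 0.961 | 0.981 | 0.995 |
| 25% | 0.986 | 0.992 | 0.996 | 0.999 |

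At 20% the largest gain is 0.995 − 0.939 = 0.056. The reported rate still shifts: at p = 20% and q = 5% it is 0.20 + 0.80 × 0.05 = 24%.

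**Missing confirmation.** Suppose a share f of any-time falls would not be confirmed (also assumed). The confirmed rate is p(1 − f):

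| Any-time rate p | Unconfirmed counted | f = 5% | f = 10% | f = 20% |
|---|---|---|---|---|
| 10% | 0.469 | 0.429 | 0.388 | 0.306 |
| 20% | 0.939 | 0.921 | 0.897 | 0.833 |

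**Efficacy set (minor).** Sections 7.1.1, 11.0, 11.1, 11.4 and 11.6.1 do not describe one population: 7.1.1 needs two post-start PSA values, the Per Protocol (efficacy sample) row of 11.4 needs one, and its Evaluable row needs none. With 4 responders at level 3, 37 patients succeed (0.953) and 38 fail (0.948), so three extra patients in the denominator would be needed to change the result.

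**The case against.** **Confirmation is already specified.** This is one combined document. Section 7.2.2 defines the term that 11.2.1 uses, and 2.4.2 and the synopsis invoke PCWG3. A separate 50% reduction among the synopsis's secondary endpoints makes most sense if the primary one is confirmed. This largely stands: a reader might infer from 11.2.1 that the sponsor chose an unconfirmed endpoint, but the document as a whole does not support that. What remains is a conflict of wording in the section that governs the analysis.

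**Response before progression is implied.** Exempting early PSA rises in 7.2.2 has a purpose only if progression otherwise matters to response. Sections 7.1.1 and 7.2.5 point the same way, and the objective in 2.1 concerns the combination. So a reader should not infer that the plan means to credit later drugs. But none of these passages says that a response must come before progression, end of treatment or new therapy, while 2.4.2 and 11.2.1 both say it may come at any time. The limit at progression in 7.2.1.3 belongs to lesion-based best overall response. The 5.3 clause on local intervention is discretionary and does not cover later systemic therapy.

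**The sizes rest on assumed rates.** This stands. A later fall must also reach half of the pre-study baseline, not half of the PSA at progression. The level 3 prior mean is 25%, and three of the four response sets in Table 1B have level 3 rates of 20% to 35%, where the later-therapy effect is small. The fourth has 10%, where it is not. Placing all 35 patients at level 3 is a simplification; Appendix E reports toxicity in the first two patients treated there.

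**Conclusion.** The point holds as a wording correction that should be made to the primary endpoint. Section 11.2.1 conflicts with 7.2.2 on confirmation, and the window has no explicit end beyond the early-progressor rule in 7.1.1.

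A reader might infer that the success decision is unreliable in general. The figures do not support this. Distortion from later therapy is large only at true rates of about 5% to 10% and is at most about 6 points at 20% or more. The reported response rate, which is what the phase II objective sets out to estimate, is exposed at every level.

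The textual conflict is certain. How often unconfirmed or later-therapy falls would occur cannot be found from the documents.

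**What to change.** 1. State the confirmed 7.2.2 definition in 11.2.1 and 11.6.1, and align 2.4.2 and the synopsis.
2. Count only PSA values, both first and confirming, up to the earlier of the Safety Follow-up/EOT visit and the start of a new anticancer therapy. A patient without a confirmed response by then is a non-responder. This also settles when the endpoint is final for the analysis in 11.1.
3. If radiographic progression is also to close the window, say how PSA values between a first bone scan with new lesions and its confirmatory scan are handled. Section 7.2.4 keeps the patient on study for those 12 weeks and then dates progression back to the first scan, so those values could otherwise be discarded without notice.
4. Name one efficacy set in 7.1.1, 11.0, 11.1, 11.4 and 11.6.1 (minor).
5. Report the unconfirmed 50% decline as the secondary measure already in the synopsis.

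**Cost.** Wording, plus probably one CRF date for the start of new anticancer therapy, since the medications row of the schedule appears blank at EOT and follow-up. The EOT limit uses a PSA already scheduled. The reported rate may be somewhat lower: responses after EOT, a first fall seen only at EOT, and falls lacking a confirming PSA all count as non-response.
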